# For Both Dose Escalation and Expansion:

- 2. Must be  $\geq 18$  years of age.
- 3. Subject must sign an informed consent form (ICF) indicating that he or she understands the purpose of and procedures required for the trial and is willing to participate in the trial prior to any trial related assessments or procedures. Where required by local or country specific regulations, each subject must sign a separate informed consent form if he or she agrees to provide samples for the subject is still eligible to

participate in the trial.

- 4. Must have measurable disease according to response assessment criteria relevant to the tumor type (eg, RECIST v1.1 [see Appendix 2]).
- 5. Must have an Eastern Cooperative Oncology Group Performance Status (ECOG-PS) score of 0-1 (see Table 14) at Screening and on C1D1. Note: Do not perform C1D1 ECOG-PS if within 5 days of Screening ECOG-PS. C1D1 ECOG-PS must be within 0-1 or subject cannot receive GEN1044.

Genmab

Document Name: GCT1044-01 Protocol Document Number: TMF-34513

Version: 4.0

- 6. Criterion modified per Amendment 3.
  - 6.1 Must have acceptable laboratory parameters according to the table below:

Parameter	Result
Acceptable renal function	GFR ≥30 mL/min (estimated using Cockcroft-Gault formula, see Appendix 4)
Acceptable liver function	
- Bilirubin	Total bilirubin ≤3.0×ULN a
Acceptable hematological status	
- Hemoglobin	≥5.6 mmol/L (9.0 g/dL) b
- ANC	≥1500/µL (1.5×10  /L)
- Platelet count	≥100×10  /L

ALT = alanine aminotransferase; ANC = absolute neutrophil count; AST = aspartate aminotransferase; GFR = glomerular filtration rate; ULN = upper limit of normal.

- 7. A woman of reproductive potential must agree to use adequate contraception during the trial and for 4 months after the last GEN1044 administration. Adequate contraception is defined as highly effective methods of contraception (please refer to Appendix 1 for more information). In countries where 2 highly effective methods of contraception are required, both methods will be required for inclusion.
- 8. A woman (of childbearing potential) must have a negative serum (beta-human chorionic gonadotropin [beta-hCG]) at screening. Subjects that are postmenopausal or permanently sterilized (see Appendix 1) can be considered as not having reproductive potential.
- 9. A woman must agree not to donate eggs (ova, oocytes) for the purposes of assisted reproduction during the entire trial, until 4 months after last treatment.
- 10. A man who is sexually active with a woman of childbearing potential and has not had a vasectomy must agree to use a barrier method of birth control, eg, either condom with spermicidal foam/gel/film/cream/suppository or partner with occlusive cap (diaphragm or cervical/vault caps) with spermicidal foam/gel/film/cream/suppository, and all men must also not donate sperm during the trial and for 4 months after receiving the last dose of GEN1044.
- 11. Criterion modified per Amendment 3.
  - 11.1 Subject must provide a tumor tissue sample during the screening period and prior to C1D1. A fresh biopsy obtained during Screening may be provided; if a fresh biopsy cannot be obtained, the most recent archival tissue can be submitted if acquired ≤6 months prior to C1D1. In case it is not feasible to meet the required criteria in escalation or expansion for fresh or archival tumor biopsy, the sponsor medical monitor's approval for enrollment is needed.

a. Except in subjects with Gilbert's syndrome, then direct bilirubin  $\leq 2 \times ULN$ .

b. Must be met without erythropoietin dependency and without transfusion within 2 weeks prior to C1D1.

Version: 4.0

#### 5.2 Exclusion Criteria

Any potential subject who meets any of the following criteria will be excluded from being assigned to treatment in the trial.

# For Both Dose Escalation and Expansion:

- 1. Has an uncontrolled intercurrent illness, including but not limited to:
  - a. Ongoing or active infection requiring intravenous treatment with anti-infective therapy that has been administered less than 2 weeks prior to first dose.
  - b. Symptomatic congestive heart failure (grade III or IV as classified by the New York Heart Association), unstable angina pectoris or cardiac arrhythmia.
  - c. Has a marked baseline prolongation of QT/QTc interval (eg, repeated demonstration of a QTc interval >480 milliseconds (ms) (CTCAE grade 1) using Fridericia's QT correction formula.
  - d. Uncontrolled hypertension defined as systolic blood pressure ≥160 mmHg and/or diastolic blood pressure ≥100 mmHg, despite optimal medical management.
  - e. Ongoing or recent (within 1 year) evidence of significant autoimmune disease that required treatment with systemic immunosuppressive treatments, which may suggest risk for immune-related adverse events (irAEs). *Note: The following conditions are not exclusionary:* Childhood asthma that has resolved, residual hypothyroidism that required only hormone replacement or psoriasis that does not require systemic treatment.
  - f. Subjects with a history of grade 3 or higher irAEs that led to treatment discontinuation of a checkpoint inhibitor should be excluded. Subjects with irAEs below grade 3 that led to discontinuation should be discussed with the sponsor.
  - g. Subjects with a prior history of myositis, Guillain-Barré syndrome, or myasthenia gravis of any grade are excluded.
  - h. History of chronic liver disease or evidence of hepatic cirrhosis.
  - i. History of non-infectious pneumonitis that has required steroids, or currently has pneumonitis.
  - j. History of organ allograft (except for corneal transplant) or autologous or allogeneic bone marrow transplant, or stem cell rescue within 3 months prior to the first dose of GEN1044.
  - k. Serious, non-healing wound, skin ulcer (of any grade), or bone fracture.
- 2. Any history of intracerebral arteriovenous malformation, cerebral aneurysm, new (within the last 6 months) or symptomatic brain metastases or stroke. (Transient ischemic attack >1 month prior to screening is allowed.)
  - a. Subjects with brain metastases must not be undergoing acute corticosteroid therapy or steroid taper. Chronic steroid therapy is acceptable provided that the dose is stable for the last 14 days prior to screening ( $\leq$  10 mg prednisone daily or equivalent).
  - b. Subjects with CNS symptoms should undergo a computed tomography (CT) scan or magnetic resonance imaging (MRI) of the brain to exclude new or progressive brain metastases. Spinal cord metastasis is acceptable. However, subjects with spinal cord compression should be excluded.

Genmab

Document Name: GCT1044-01 Protocol Document Number: TMF-34513

Version: 4.0

- 3. Criterion modified per Amendment 3.
  - 3.1 Prior therapy and prophylaxis:
    - a. Radiotherapy: Radiotherapy within 14 days prior to first GEN1044 administration. Palliative radiotherapy will be allowed.
    - b. Treatment with an anti-cancer agent (within 28 days or after at least 5 half-lives of the drug, whichever is shorter), prior to GEN1044 administration. Accepted exceptions are bisphosphonates (eg, pamidronate, zoledronic acid) and denosumab.
    - c. Received any investigational agent (including investigational vaccines) or used an invasive investigational medical device within 28 days before the planned first dose of GEN1044 or is currently enrolled in an interventional trial.
      - Note: Subjects who are in the follow-up phase of an interventional trial may participate if the subject has not received an investigational agent within 28 days prior to the first dose of GEN1044.
    - d. Prophylaxis with live, attenuated vaccines within 3 weeks prior to first dose of GEN1044; or prophylaxis with the first and/or second injection of SARS-CoV-2 nucleic acid vaccine within 30 days prior to first dose of GEN1044.
    - e. Chronic systemic immunosuppressive corticosteroid doses, ie, prednisone >10 mg daily or a cumulative dose >150 mg prednisone within 14 days before the first GEN1044 administration. Replacement therapy (eg, thyroxine, insulin, or physiologic corticosteroid replacement therapy for adrenal or pituitary insufficiency) is not considered a form of systemic treatment and is permitted.
    - f. Received granulocyte-colony stimulating factor (G-CSF) or granulocyte/macrophage-colony stimulating factor support 4 weeks prior to first GEN1044 administration or is chronically transfusion dependent.
    - g. Any prior therapy with a compound targeting CD3.
    - h. Treatment with chimeric antigen receptor T cell (CAR-T) therapy within 30 days prior to first dose of GEN1044.
- 4. Toxicities from previous anti-cancer therapies that have not resolved to baseline levels or to grade 1 or less, with the exception of alopecia, anorexia, vitiligo, fatigue, hyperthyroidism, hypothyroidism, and peripheral neuropathy. Anorexia, hyperthyroidism, hypothyroidism, and peripheral neuropathy must have recovered to ≤ grade 2.
- 5. Known past or current malignancy other than inclusion diagnosis, except for
  - a. Cervical carcinoma of Stage 1B or less.
  - b. Non-invasive basal cell or squamous cell skin carcinoma.
  - c. Non-invasive, superficial bladder cancer.
  - d. Prostate cancer with a current prostate-specific antigen (PSA) level <0.1 ng/mL.
  - e. Any curable cancer with a complete response (CR) of >2 years duration.

Version: 4.0

- 6. Criterion modified per Amendment 3.
  - 6.1 Has a history of ≥ grade 3 allergic reactions to monoclonal antibody therapy as well as known or has known allergies, hypersensitivity, or intolerance to GEN1044 or its excipients (refer to the GEN1044 Investigator's Brochure).
- 7. Has any condition for which, in the opinion of the investigator or the sponsor, participation would not be in the best interest of the subject (eg, compromise the well-being) or that could prevent, limit, or confound the protocol-specified assessments.
- 8. Has had major surgery, (eg, requiring general anesthesia) within 4 weeks before screening, or will not have fully recovered from surgery, or has surgery planned during the time the subject is expected to participate in the trial. **Note:** Subjects with planned surgical procedures to be conducted under local anesthesia may participate.
- 9. Known history of seropositivity for human immunodeficiency virus (HIV).
- 10. Known history/positive serology for hepatitis B (unless immune due to vaccination or resolved natural infection or unless passive immunization due to immunoglobulin therapy):
  - a. Positive test for hepatitis B surface antigen (HBsAg) or for antibodies to hepatitis B core antigens (anti-HBc)

#### and

- b. Negative test for antibodies to hepatitis B surface antigens (anti-HBs).
- 11. Known medical history or ongoing hepatitis C infection that has not been cured.
- 12. Substance abuse, medical, psychological, or social conditions that may interfere with the subject's participation in the trial or evaluation of the trial result.
- 13. Has been dosed in this trial before.
- 14. Is a woman who is pregnant or breast-feeding.
- 15. Seizure disorder requiring therapy (such as steroids or anti-epileptics).

# 5.3 Screening Failures

Screening failures are defined as subjects who consent to participate in the clinical trial but do not meet the protocol-defined eligibility criteria (see Section 5.1 and Section 5.2). A minimal set of screening failure information is required to ensure transparent reporting of screening failure subjects to meet the Consolidated Standards of Reporting Trials (CONSORT) publishing requirements. Minimal information includes demography, screening failure details, eligibility criteria, and any SAE. (Refer to definition of SAE [Section 10.1.2] and AE reporting [Section 10.2] for additional information.)

Individuals who do not meet the criteria for participation in this trial (screening failures) may be rescreened once. The rescreening must be approved by the sponsor to ensure that the safety of the subject is not compromised. Upon rescreening, all eligibility criteria must be re-assessed by the investigator. Results from assessments performed during the previous screening period are acceptable for rescreening purposes if performed within the specified time frame and the inclusion/exclusion criteria are met.

Version: 4.0

Genmab

Upon rescreening, the subject must complete a full new screening visit and all eligibility criteria must be re-assessed at the rescreening visit. A new screening number will not be allocated to the subject at rescreening.

Version: 4.0

#### 6 TREATMENT

# 6.1 Treatment Assignment or Randomization

# 6.1.1 Subject Numbering

After signing the ICF, subjects will be assigned a unique subject identification number before undergoing any screening procedure(s).

# **6.1.2** Treatment Assignment

A subject will be assigned to IV administration of GEN1044 with a defined priming dose, intermediate dose(s), and defined subsequent full (fixed) doses (see Section 4.2 [Dose Escalation] and Section 4.3 [Expansion]).

# For Dose Escalation part:

Subjects will be assigned to a DL cohort in the order in which they become eligible for treatment assignment, using a manual assignment method provided by the sponsor or its contract research organization (CRO). For the Dose Escalation, site personnel must contact the CRO when a potential subject has been identified. If there is an opening in the currently enrolling dose level, the site will be given approval to start the screening process. If there is no opening, the subject will be placed on a waiting list, and the site will be alerted of the next available opening either in the currently enrolling dose level or at the next opened dose level.

Refer to the laboratory manual for additional information and stepwise guidance on enrollment procedures.

# For Expansion part:

Subjects will be allocated to the appropriate expansion cohort (Expansion Cohorts 1 through 8), based on the type of cancer (see Section 4.3). For each group, subjects will be allocated in the order in which they become eligible for treatment assignment, using an interactive response technology (IRT) system. Refer to the laboratory manual for additional information and stepwise guidance on enrollment procedures.

#### 6.2 Premedication Prior to GEN1044 Administration

The purpose of the prophylactic premedication is to mitigate risk and severity of infusion-related reactions (IRRs) and CRS. Premedication with corticosteroids, antihistamines, and antipyretics (Table 12) is mandatory 30 to 120 minutes prior to the first 3 administrations of GEN1044 in Cycle 1, ie, the first, second, and third administrations in the Dose Escalation part and in the Expansion part. If CRS  $\geq$  grade 2 occurs following the third administration (C1D15), prophylactic premedication should be continued and administered at the fourth administration (C2D1) and onwards until CRS events do not occur. If a grade 1 CRS event or no CRS event occurs following the third administration (C1D15), then prophylactic premedication should not be administered for subsequent GEN1044 administrations.

Corticosteroid administration can be either IV or oral including pre-medication administration (Table 12) with the recommended dose or equivalent (Appendix 3).

Version: 4.0

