ECOG-PS	Do not perform C1D1 ECOG-PS if within 5 days of Screening ECOG-PS. C1D1 ECOG-PS must be within 0-1 or subject cannot receive GEN1044. At Unscheduled visit, only if relevant.	9.3.5	X	X									X						

Document Number: TMF-34513

Treatment Cycle (C)	Notes	Section Reference	Screening					Cyclo	e 1							Cycle	2		
Day (d)/Week (wk)			≤ 28d prior to C1 (1d)	1d	2d	4d	8d	9d	11d	15d	16d	18d	1d	2d	4d	8d	9d	11d	15d
Visit window							+1d			+1d			+2d			+2d			+2d
Adverse Events	See footnote "b." Report all AEs from first GEN1044 dose (C1D1) until 30 days after the last GEN1044 dose (ie, Safety Follow-up visit). After SFU only report suspected GEN1044-related SAEs.	10.1, 10.2	Xb	X	X	X	X	X	X	X	X	X	X	X	X	X		X	X
Concomitant Medication		6.5, 9.1.4	X	X	X	X	X	X	X	X	X	X	X	X	X	X		X	X
Premedication with Corticosteroids, Antihistamines and Antipyretics	Premedication is mandatory 30 to 120 minutes prior to first 3 administrations of GEN1044.	6.2, 6.5		X			X			X									
GEN1044 Administration g		6.3, 6.6		X			X			X			X			X			X
LABORATORY AS	SSESSMENTS																		
Hematology	At Unscheduled visit, only if relevant.	9.4	Xc	X	X	X	X	X	X	X	X	X	X			X			X
Biochemistry	At Unscheduled visit, only if relevant.	9.4	Xc	X	X	X	X	X	X	X	X	X	X		X	X		X	X
Coagulation factors	At Unscheduled visit, only if relevant.	9.4	Xc										X						
Urinalysis	At Unscheduled visit, only if relevant.	9.4	X c																
Pregnancy test	At Unscheduled visit, only if relevant.	9.4	X c																
Hepatitis B	At Unscheduled visit, only if relevant.	9.4	Xc																
T3, T4	At Unscheduled visit, only if relevant.	9.4	Xc																
PK/ADA sampling	See Table 2	9.5, 9.6																	
Tumor biopsy, biomarkers	See Table 8	9.7																	
PSA	Subjects with prostate cancer; central lab	9.2.2	Xc	X									X						
Serum testosterone	Subjects with prostate cancer; central lab	9.4.1	Xc																

Document Number: TMF-34513

 Table 1
 Visit Evaluation Schedule - Dose Escalation Part (Continued)

Treatment Cycle (C)	Notes	Section Reference	Cycle	3 to C	ycle 4	Cyc	le 5 to	PDf	Treatment Discontin- uation visit	Safety Follow-up visit	Survival Follow-up	Unscheduled
Day (d)/Week (wk)			1d	8d	15d	1d	8d	15d	-	30d after last dose	Every 12 wk after last dose	
Visit window			+3d	+1d	+3d	+3d	+3d	+3d		+14d	+7d	
Body weight		9.3.2							X			

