- e. Starting with C3, obtain labs ≤3 days before D1. Central lab: PSA; local lab: hematology, biochemistry, coagulation factors, urine pregnancy test, and urinalysis.
- f. Subjects in cohorts receiving 1 interim dose will receive: A priming dose on C1D1; an intermediate dose on C1D8; and the first full dose on C1D15. Subjects in cohorts receiving 2 interim doses will receive: A priming dose on C1D1; intermediate doses on C1D8 and C1D15; and the first full dose on C2D1.

Document Number: TMF-34513

Version: 4.0

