**Table 12 Mandatory CRS Prophylaxis** 

			Glucocorticosteroids	Antihistamines	Antipyretics
	1st GEN1044 administration	Day 01*	Prednisolone 100 mg IV†	Diphenhydramine 50 mg IV or PO (or equivalent)	Paracetamol (acetaminophen) 650 to 1000 mg PO (or equivalent)
Cycle 1	2 nd GEN1044 administration	Day 08*	Prednisolone 100 mg IV†	Diphenhydramine 50 mg IV or PO (or equivalent)	Paracetamol (acetaminophen) 650 to 1000 mg PO (or equivalent)
	3 rd GEN1044 administration	Day 15*	Prednisolone 100 mg IV†	Diphenhydramine 50 mg IV or PO (or equivalent)	Paracetamol (acetaminophen) 650 to 1000 mg PO (or equivalent)
Cycle 2	4 th GEN1044 administration	Day 01*	Yes, if CRS ≥ grade 2 occurred following the 3 rd GEN1044 administration at C1D15, administration of glucocorticosteroids is continued in Cycle 2 until no subsequent CRS develops.	Yes, if glucocorticosteroids are administered	Yes, if glucocorticosteroids are administered

\* 30 minutes to 2 hours prior to administration of GEN1044.

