# 6.5 Concomitant Medications and Therapies

The subject must be told to notify the trial site about any new medications (including over-the-counter or prescription medicines, vitamins, and vaccines) they take after the start of GEN1044. All medications (other than GEN1044) and significant non-drug therapies (including physical therapy, herbal/natural medications and blood transfusions) administered during the trial (ie, beginning with administration of the first dose of trial drug until 30 days after the last dose of trial drug) must be documented.

Investigators may prescribe concomitant medications or treatments deemed necessary to provide adequate supportive care except for those medications identified as "prohibited" (Section 6.5.3).

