#### 7 DOSE MODIFICATIONS AND SAFETY MANAGEMENT GUIDELINES

# 7.1 **Dose-Limiting Toxicity**

The DLT evaluation period is defined as the period from the start of the first GEN1044 administration on C1D1 of the Dose Escalation part of the trial until 7 days after the first full dose. As described in Section 4.1, if a subject receives the priming dose on C1D1, one intermediate dose on C1D8, and the full dose starting on C1D15, the DLT period will be the first 21 days of Cycle 1 (Cycle 1 days 1 through 21). If a subject receives the priming dose on C1D1, the first intermediate dose on C1D8, the second intermediate dose on C1D15, and the first full dose on C2D1, the DLT period will be Cycle 1 up to and including C2D7 (ie, a total of 28 days). The DLT evaluation period may be adjusted for potential GEN1044 treatment delay as described in Section 11.1.7.

National Cancer Institute (NCI) Common Terminology Criteria for Adverse Events (CTCAE) v5.0 (NCI-CTCAE, 2017) will be used to assess toxicities/AEs, except for CRS and immune effector cell-associated neurotoxicity syndrome (ICANS) (see Section 10.4.1 and Section 10.4.2, respectively).

A DEC is set up for the study. The DEC will review data from each DL cohort and make a decision regarding dose escalation. That decision of the DEC has to be confirmed by the sponsor SC. The DMC will review data on a quarterly basis.

Events to be collected and assessed by the DMC for DLTs include: SAEs; AESIs where applicable; and clinically significant abnormal laboratory values (that are not already covered by a separate AE term).

The occurrence of any of the toxicities outlined in this section will be considered a DLT if assessed by the investigator to be at least possibly related to GEN1044. AEs clearly not related to the trial treatment (GEN1044) such as disease progression, environmental factors, unrelated trauma, etc, should not be considered a toxicity event.

The following will qualify for a DLT:

- ≥ Grade 3 CRS, graded according to American Society for Transplantation and Cellular Therapy (ASTCT) criteria (Lee et al., 2019) (see Section 10.4.1, Table 16).
- \geq Grade 3 ICANS, graded according to the criteria specified in Table 17, Section 10.4.2.
- Any Grade 3 or 4 non-hematologic toxicity except for:
  - Grade ≥ 3 nausea/vomiting or diarrhea <72 hours with adequate anti-emetic and other supportive care
  - Grade  $\geq$  3 fatigue  $\leq$ 1 week

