# 7.2 GEN1044 Dose Modification Guidance and Safety Stopping Criteria

#### 7.2.1 Dose Escalation Part

- In the event a subject experiences an AE that meets DLT criteria as outlined in Section 7.1, treatment must be permanently discontinued (unless the subject per investigator's discretion has recovered or is expected to recover and expected to benefit from continued treatment). GEN1044 should also be held for the following:
  - If platelet count  $<50\times10^9$ /L, hold dose until platelet count is  $\ge50\times10^9$ /L.
  - If febrile neutropenia  $<0.5\times10^9$ /L, hold dose until neutrophil count is  $\ge0.5\times10^9$ /L.
  - o If hemoglobin is  $\leq 8 \text{ g/dL}$  ( $\leq 5 \text{ mmol/L}$ ), hold dose until hemoglobin  $\geq 8 \text{ g/mL}$  ( $\geq 5 \text{ mmol/L}$ ).
  - **Note**: Transfusion with blood products and/or administration with G-CSF is permitted if needed (see Section 6.5.2.2).
- During the trial, a planned dose of GEN1044 can be postponed for up to 6 weeks for an AE, whether it is considered drug-related or not; a delay of >6 weeks requires permanent discontinuation of treatment. The delay might be extended to 12 weeks after consultation with the sponsor medical monitor.
- First episodes of cytokine blockade-refractory grade 3 CRS or ICANS (see Section 10.4.1) lasting >72 hours require permanent discontinuation from trial treatment.
- First episodes of refractory grade 4 CRS or ICANS require permanent discontinuation from trial treatment.
- Refer to Appendix 7, Table 27, for dose modification guidelines for specific adverse events. For dose escalation, these rules will only apply after the DLT period.

Version: 4.0

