# 7.2.2 Expansion Part

- In the event a subject experiences a ≥ grade 2 AE considered drug-related, the GEN1044 dose should be held until the AE resolves to ≤ grade 1. Exceptions are:
  - o Grade 2 CRS
  - Grade 2 ICANS
  - $\circ$   $\geq$  grade 2 fever attributed to CRS
  - $\circ$   $\geq$  grade 2 hypotension attributed to CRS
  - $\circ$   $\geq$  grade 2 hypoxia attributed to CRS,
  - ≥ grade 2 lymphocytopenia

If drug is held for more than 12 weeks, the subject should be permanently discontinued from therapy.

- In cases of cytokine blockade-refractory grade 3 CRS or ICANS lasting >72 hours, GEN1044 must be permanently discontinued.
- In cases of grade 4 CRS or ICANS, GEN1044 must be permanently discontinued.
- In the event a subject experiences a second episode of the same AE at ≥ grade 3, except fever/hypotension/hypoxia attributed to CRS or lymphocytopenia, GEN1044 must be permanently discontinued.
- Refer to Appendix 7, Table 27, for dose modification guidelines for specific adverse events.

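### Section 6.2 has no rule for resuming CRS premedication when grade ≥2 CRS first appears, or returns, after C2D1 or a later dose

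*Protocol*

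**What the plan says.** Section 6.2 states that premedication is meant to reduce the risk and severity of infusion-related reactions and CRS. It sets three rules.

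- **Administrations 1 to 3 (C1D1, C1D8, C1D15):** mandatory. The Schedule of Activities (Tables 1 and 5) repeats only this rule: "Premedication is mandatory 30 to 120 minutes prior to first 3 administrations of GEN1044".
- **Grade ≥2 CRS after C1D15:** premedication goes on at C2D1 and later, until CRS stops occurring. Table 12 puts it that "administration of glucocorticosteroids is continued in Cycle 2 until no subsequent CRS develops".
- **Grade 1 or no CRS after C1D15:** "then prophylactic premedication should not be administered for subsequent GEN1044 administrations". No exception follows this sentence.

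Table 12 has no row after the fourth administration (C2D1).

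**The concern.** The protocol already accepts that grade ≥2 CRS after one dose is a reason to premedicate the next: that is its rule at C1D15. It does not apply the same reasoning to later doses. A subject whose first grade ≥2 CRS comes after C2D1, or whose CRS returns after premedication was continued and then stopped, falls outside every stated rule. The only sentence that speaks to later doses in a subject who was quiet after C1D15 says not to premedicate.

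At stake is CRS prophylaxis in a first-in-human trial of a T-cell engager. A site that follows the text literally would re-dose a subject with recent grade ≥2 CRS without the protection that 6.2 requires for the same event one dose earlier.

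**Working it through.** The plan states no figure on this point, so the check is a reading of the text plus a count of doses.

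**1. Doses outside the mandatory window.** Section 6.3 gives Days 1, 8 and 15 in Cycles 1 to 4, then Day 1 only.
- Weekly administrations: 4 × 3 = 12. Mandatory premedication covers 3, leaving 12 − 3 = 9, plus every three-weekly dose from Cycle 5.
- After a first event at C2D1: 2 (C2D8, C2D15) + 3 (Cycle 3) + 3 (Cycle 4) = 8 weekly doses, plus the three-weekly doses.

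The 8 assumes the earliest possible late onset and treatment through Cycle 4. It counts doses without a rule and does not measure risk.

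**2. Two subjects with the same event one dose apart.**

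| | Subject A | Subject B |
|---|---|---|
| CRS after C1D15 | grade 2 | none |
| Premedication at C2D1 | yes (6.2, Table 12) | no (6.2) |
| CRS after C2D1 | none | grade 2 |
| Premedication at C2D8 | stops | 6.2 advises against it |

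If subject A then has grade 2 CRS after, say, C2D15, no sentence says to start again.

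**3. Does dosing continue after grade 2 CRS?**
- Section 7.1: CRS is a DLT from grade 3, so grade 2 is not.
- Section 7.2.1 (Escalation): the hold list covers platelets, febrile neutropenia and hemoglobin. Its CRS rules concern only refractory grade 3 or 4 events. A dose may be postponed for an AE by up to 6 weeks, extendable to 12, but this is optional.
- Section 7.2.2 (Expansion): after a drug-related AE of grade 2 or higher, "the GEN1044 dose should be held until the AE resolves to ≤ grade 1. Exceptions are" listed, and grade 2 CRS is among them.
- Table 27 (Appendix 7): the CRS entries begin at refractory grade 3.

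So the next weekly dose can go ahead on its planned day, 7 days later.

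**4. Grade 3.** In Escalation, "In the event a subject experiences an AE that meets DLT criteria as outlined in Section 7.1, treatment must be permanently discontinued", but an exception follows for subjects who have recovered, or are expected to, and should benefit. In Expansion, a first grade 3 CRS event forces discontinuation only if refractory to cytokine blockade for more than 72 hours; otherwise dosing can resume on recovery to grade 1 or less. Re-dosing after late grade 3 CRS is therefore possible, though less usual in Escalation.

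**5. Where else might a restart rule sit?** Section 6.5.2.1 and Appendix 6 cover treating CRS. Section 7.2 and Appendix 7 cover holding and stopping. Section 7.3 covers infusion-related reactions. None addresses prophylaxis before the next dose. The Appendix 8 diagram is not shown in the text available, but it concerns ICANS.

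**The case against.** The strongest reply is investigator discretion, and much of it stands. Section 6.5 says "Investigators may prescribe concomitant medications or treatments deemed necessary to provide adequate supportive care", apart from prohibited items, and premedication is not prohibited. Section 6.5.2 names premedication among the supportive medication a site will provide, and 6.5.3 leaves premedication steroids out of its corticosteroid limit. The sentence in 6.2 says should not, in contrast to the mandatory wording for the first three doses, and was not evidently written with a later grade ≥2 event in mind. A dose can also be postponed (7.2.1), and subjects are observed after infusion for at least 4 hours in Cycles 1 and 2 and at least 2 hours thereafter (6.3). A reader might infer that 6.2 bars premedication after late CRS; these provisions show that it does not. What remains is that a general allowance sits against specific text pointing the other way.

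Three further inferences go too far.

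- **That C1D15 alone settles all later premedication.** It settles whether premedication continues at C2D1. For subjects who continue, later CRS decides when it stops.
- **That every subject dosed at or after C2D1 is affected.** Only those with grade ≥2 CRS after C2D1 or later are.
- **That conditional premedication at C2D1 is an error when two intermediate doses are used.** The first full dose then falls at C2D1, and "the DLT period will be Cycle 1 up to and including C2D7 (ie, a total of 28 days"), so a reader might want premedication made mandatory there and recorded in the DLT table. The documents do not support this. Table 12 has an explicit C2D1 row, and Amendment 3 revised that table when it introduced the intermediate doses, so the rule looks deliberate. There are no data on how premedication at C2D1 changes CRS risk, and another 100 mg of prednisolone before a T-cell engager is a genuine trade-off. Table 29 already reports third-dose and fourth-dose DLT rates in separate rows. In SAP Table 1 the only four-step row rises 37.5/30 = 1.25-fold at C2D1, with bracketed doses; the larger steps into a first full dose (30/10 = 3-fold to 60/3 = 20-fold) fall at C1D15, where premedication is mandatory.

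**Conclusion.** The concern holds as a gap in the restart rule. Followed as written, 6.2 leads to re-dosing after late grade ≥2 CRS without the prophylaxis that the same section requires after an identical event at C1D15. Because the text states a positive instruction for later doses, this is more than missing detail.

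The documents give no count of subjects with grade ≥2 CRS after C2D1 or later, and no estimate of how much premedication lowers CRS risk at those doses. The conclusion assumes that premedication helps there too, as 6.2's stated purpose and its own rule after C1D15 imply. The practical reach is also limited by events: the SAP (1.2 and 2.2) reports that enrollment was stopped and that no expansion data were collected. The point concerns the current protocol text and anyone treated under it.

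**What to change.** In section 6.2, after the last sentence of the first paragraph, add:

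> If CRS ≥ grade 2 follows any later administration, resume premedication (Table 12) at the next administration and continue until an administration is not followed by CRS.

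Add a matching row to Table 12, labelled *Any later administration*. No change is needed to the C2D1 row or to Table 29.

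The cost is wording, plus extra premedication only in subjects with late grade ≥2 CRS. At the Table 12 dose of 100 mg prednisolone or equivalent, that is 1 × 100 = 100 mg if the next dose passes without CRS. The extreme through Cycle 4 is 8 × 100 = 800 mg, for a subject with onset at C2D1 who has CRS after every premedicated weekly dose up to at least C4D8. No visit is added.
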